3 SAMPLE SIZE AND POWER

Please refer to section 11.1 of the study protocol amendment 2.

4 STUDY POPULATION

We present in this section, the inclusion/exclusion criteria as detailed in protocol amendment 2 and compare the changes to protocol amendment 1 to take into consideration the 6 patients enrolled under protocol amendment 1.

4.1 Inclusion Criteria

Per protocol amendment 2, the following inclusion criteria had to be met to be eligible for enrolment:

1. Male or female 18 years of age or older
2. Diagnosis of at least two episodes of recurrent pericarditis
3. At least 1 day with pericarditis pain ≥ 4 on the 11-point NRS within prior 7 days
4. One of
 - a. CRP level ≥ 1.0 mg/dL within prior 7 days OR
 - b. Evidence of pericardial inflammation assessed by delayed pericardial hyperenhancement on cardiac magnetic resonance imaging (CMR)
5. Currently receiving non-steroidal anti-inflammatory drugs (NSAIDs) and/or colchicine and/or corticosteroids for treatment of pericarditis (in any combination) in stable doses

6. Male patients with partners of childbearing potential who have had a vasectomy or are willing to use double barrier contraception methods during the conduct of the study and for 2 months after the last dose of study drug.
7. Women of childbearing potential willing to use an acceptable method of contraception starting with study drug administration and for a minimum of 2 months after study completion. Otherwise, women must be postmenopausal (at least 1 year absence of vaginal bleeding or spotting and confirmed by follicle stimulating hormone [FSH] ≥ 40 mIU/mL [or ≥ 40 IU/L] if less than 2 years postmenopausal) or be surgically sterile.

4.2 Exclusion Criteria

Patients meeting any of the following criteria were not eligible to participate:

1. Diagnosis of pericarditis that is secondary to specific prohibited etiologies, including tuberculosis (TB); neoplastic, purulent, or radiation etiologies; post-thoracic blunt trauma (e.g., motor vehicle accident); myocarditis
2. Estimated glomerular filtration rate (eGFR) <30 mL/min
3. Elevated alanine aminotransferase (ALT) or aspartate aminotransferase (AST) > 5 times the upper limit of normal (ULN) or ALT or AST >3 x ULN plus bilirubin >2 x ULN
4. Sepsis, defined as documented bacteremia at the time of screening or other documented active infection
5. Prior history of sustained ventricular arrhythmias
6. History of QT interval prolongation
7. QTc interval > 500 msec (please refer to Section 9.2.3 for bundle branch block, bifascicular block and paced rhythm correction)
8. Current participation in any research study involving investigational drugs or device
9. Inability or unwillingness to give informed consent
10. Ongoing drug or alcohol abuse
11. On any cannabinoid during the past month
12. Women who are pregnant or breastfeeding
13. Current diagnosis of cancer, with the exception of non-melanoma skin cancer

14. Any factor, which would make it unlikely that the patient can comply with the study procedures
15. Showing suicidal tendency as per the C-SSRS, administered at screening
16. On digoxin and/or type 1 or 3 antiarrhythmics
17. On immunosuppressive therapy with any of the following:
 - a. Rilonacept
 - b. Anakinra
 - c. Canakinumab
 - d. Methotrexate
 - e. Azathioprine
 - f. Cyclosporine
 - g. IVIG

Difference between protocol amendments 1 and 2 re the selection criteria and the (potential) impact on the statistical Analysis

- Inclusion criterion #5 in Amendment 1 was as follows: Has received NSAIDs and/or colchicine and/or corticosteroids (in any combination) in stable doses for at least 3 days prior to enrolment
- Exclusion criteria 5 and 16 were not present in protocol amendment 1

Potential Impact on statistical Analysis Plan:

Patients included under protocol amendment 1 will be reviewed during Data Review Meeting to ascertain if they complied with protocol amendment 2 with respect to inclusion criterion 5 and exclusion criteria 5 and 16 per protocol amendment 2.

4.3 Study treatment assignment

Per protocol amendment 2, eligible patients would receive open label IMP (i.e. CardiolRxTM).

The dosing regimen was as follows:

- Day 1 p.m. to Day 3 a.m. dose: 5 mg/kg of body weight b.i.d. First dose to be taken in the evening of the screening visit (i.e. day 1)
- Day 3 p.m. dose to Day 10 a.m. dose: 7.5 mg/kg of body weight b.i.d. Dose titration if previous dose tolerated
- Day 10 p.m. dose to end of treatment period (a.m. dose at either week 8 or am dose week 26 if patient continued in the EP phase of the trial): 10 mg/kg of body weight b.i.d. Dose titration if previous dose tolerated

The morning and evening doses should be taken minimally 6 and maximally 18 hours apart. If the next higher dose after each study drug increase was not tolerated, the site could reduce the dose to the previous tolerated dose.

Difference between protocol amendments 1 and 2 and the (potential) impact on the statistical Analysis

Protocol amendment 1: Administration of IMP was planned as follows²:

- Day 1 p.m. dose to Day 3 a.m. dose: 2.5 mg/kg of body weight b.i.d.
- Day 3 p.m. dose to Day 7 a.m. dose: 5.0 mg/kg of body weight b.i.d.
- Day 7 p.m. dose to Day 14 a.m. dose: 7.5 mg/kg of body weight b.i.d.
- Day 14 p.m. dose to end of treatment period (a.m. dose at week 26, i.e Day 181): 10.0 mg/kg of body weight b.i.d

Impact on the statistical Analysis Plan:

The difference in the overall dose is an increase of 5% (i.e. starting dose was 2.5 mg/kg of body weight b.i.d for protocol amendment 1 and 5 mg/kg of body weight b.i.d for amendment 2). This may potentially impact on the primary endpoint at 8 weeks and on the total dose taken over the study duration.

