2.2 Study Objectives

The primary objective was to evaluate the effect of treatment with CardiolRx™ on recurrent pericarditis.

The primary safety objective was to demonstrate that administration of CardiolRx™ in the proposed doses in this patient population is safe.

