8.2 Patient enrolment and disposition

Patient enrolment by site will be tabulated by protocol amendment and overall.

Patient disposition will be summarized by protocol amendment and overall. This will include # screened (i.e. with informed consent), # screening failures with reason, # enrolled and # who started IMP. The summary will include the number and percentage of patients in each of the defined analysis populations in Section 5. In addition, frequency counts and percentages of patients' reported reasons for ending the study will be summarized.

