8.6.1 Adverse events (AEs)

The number of adverse events and percentage of patients with at least one adverse event will be summarized by system organ class and by preferred terms (MedDRA).

AEs will be considered as treatment - emergent adverse events (TEAE) if the event onset time (and date) is $>$ start of the IMP. Adverse events with incomplete onset dates will be summarized as TEAE regardless of severity and relationship to the IMP.

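### SAP 4.3's 5% dose difference between amendments holds to Week 8 only; the titration-phase gap is far larger, and no early safety summary is planned by amendment

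*SAP*

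**What the plan says.** SAP 4.3 prints both titration schedules and then sizes the change: "The difference in the overall dose is an increase of 5" per cent. It explains the figure only by the starting dose, 2.5 against 5 mg/kg b.i.d., and gives no period. It continues: "This may potentially impact on the primary endpoint at 8 weeks and on the total dose taken over the study duration".

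SAP section 4 says that the eligibility comparison is made "to take into consideration the 6 patients enrolled under protocol amendment 1". SAP 8.2 carries the amendment through to reporting: "Patient disposition will be summarized by protocol amendment and overall". SAP 8.4 defines planned dose separately for each amendment.

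The safety sections do not follow that pattern. SAP 8.6.1 says "The number of adverse events and percentage of patients with at least one adverse event will be summarized by system organ class" and by preferred term, with no mention of amendment. The rest of SAP 8.6 and the titles of Tables 24 to 33 are also silent on it. SAP 4.5 notes that the changed visit timing may affect the laboratory and ECG endpoints. Its response is to combine the amendment 1 Week 2 and amendment 2 Week 3 laboratory, vital sign and ECG data under one label, Week 2-3. The safety objective in SAP 2.2 is to "demonstrate that administration of CardiolRx™ in the proposed doses in this patient population is safe".

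**The concern.** A cumulative percentage shrinks as follow-up lengthens, because both schedules end on the same 10 mg/kg b.i.d. and the absolute gap stops growing once both groups are there. One figure without a horizon therefore says little about the first two weeks, when patients step up and when tolerance of each step is judged. In that window the two schedules differ most.

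The SAP recognises that the amendments may affect results, but the planned safety output does not let a reader look at the schedules separately. If early events or ECG changes depend on how fast the dose rises, the pooled tables will describe neither titration. If they do not depend on it, the pooled tables cannot show that either. The protocol's rationale gives tolerance and safety as a purpose of the pilot and says that it will inform the feasibility of a randomized withdrawal trial.

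**Working it through.** **Inputs.** Dose steps are from SAP 4.3 and day counts from the planned-dose formulas in SAP 8.4.

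- Amendment 1: 2.5 mg/kg b.i.d. for 2 days ("Day 1 p.m. dose to Day 3 a.m. dose: 2.5 mg/kg of body weight b.i.d"), 5 for 4 days ("Day 3 p.m. dose to Day 7 a.m. dose: 5.0 mg/kg of body weight b.i.d"), 7.5 for 7 days, then 10 for 43 days to Week 8 or 167 days to Week 26.
- Amendment 2: 5 mg/kg b.i.d. for 2 days, 7.5 for 7 days, then 10 for 47 days to Week 8 or 171 days to Week 26.

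**Formula.** Cumulative planned dose per kg = sum of (days × mg/kg b.i.d. × 2). Difference = amendment 2 / amendment 1 − 1.

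**Reproducing the SAP's figure (Week 8, 56 days).**

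- Amendment 1: 10 + 40 + 105 + 860 = 1015 mg/kg.
- Amendment 2: 20 + 105 + 940 = 1065 mg/kg.
- 1065/1015 − 1 = 4.9%, which rounds to the stated 5%.

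**Other horizons.**

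| To | Amendment 1 (mg/kg) | Amendment 2 (mg/kg) | Gap | Difference |
|---|---|---|---|---|
| Day 3 a.m. | 10 | 20 | 10 | +100% |
| Day 7 a.m. | 50 | 80 | 30 | +60% |
| Day 14 a.m. | 155 | 205 | 50 | +32% |
| Week 8 | 1015 | 1065 | 50 | +4.9% |
| Week 26 (180 days, as in SAP 8.4) | 3495 | 3545 | 50 | +1.4% |

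**Where the gap arises.** Days 1 to 3: 2 × 2.5 × 2 = 10 mg/kg. Days 3 to 7: 4 × 2.5 × 2 = 20. Days 7 to 10: none, as both are on 7.5. Days 10 to 14: 4 × 2.5 × 2 = 20. The starting dose, the only reason that the SAP gives, accounts for 10 of the 50 mg/kg.

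**The merged Week 2-3 row.** I assume that the visits fall on their nominal days, Day 14 and Day 21.

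- Amendment 1, Week 2: the move to 10 mg/kg comes with the Day 14 evening dose, so an ECG after that morning's dose is on 7.5 mg/kg b.i.d., with 155 mg/kg cumulative.
- Amendment 2, Week 3: 11 days at 10 mg/kg b.i.d., with 20 + 105 + 220 = 345 mg/kg cumulative.

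The row thus mixes two scheduled dose levels and a cumulative exposure ratio of 345/155 = 2.2. An amendment 1 visit held after Day 14 would narrow the contrast.

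**Two side points.** Dividing the printed 8-week values in SAP 8.4 (1.11/1.07) gives 3.7%, because 1065/950 = 1.121 and should print as 1.12. The divisor of 950 mg/mL also differs from the 100 mg/mL concentration in protocol 6.4 and 8.1. It cancels in these ratios, but the two passages need reconciling.

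**The case against.** The strongest reply is that 5% is not an error. It is the Week 8 value, and Week 8 is the horizon of the primary endpoint and the staged analysis, and the first that the SAP's next sentence names. Both schedules are printed in full, and planned totals by amendment at 8 and 26 weeks are in SAP 8.4. No analysis uses the 5%, and the SAP does not cite it to justify pooling. All of this stands. On its own, the wording change would be close to clerical.

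A reader might infer more than the documents support:

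- *That the SAP separates only enrolment and disposition by amendment.* It also has amendment-specific planned-dose formulas and reviews amendment 1 patients against the changed eligibility criteria at the Data Review Meeting. Neither splits a safety result.
- *That pooling hides a known amount of toxicity.* Suppose, by assumption, early event rates of 10% on the slower and 30% on the faster schedule, with 6 and 19 of 25 patients. The pooled rate is (6 × 0.10 + 19 × 0.30)/25 = 25%. With 5% and 40% it is 32%. With equal rates nothing shifts, and reversed rates would shift it the other way. The documents give no such rates, and the planned adverse event tables are not limited to early onset, so they would not show these figures.
- *That the doses in the safety objective mean only the amendment 2 titration.* Both schedules have the same 10 mg/kg target, and the text does not settle this.

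Two further cautions stand. The absence of a split is inferred from section text and table titles, since no table shells are given and part of the exposure text in SAP section 7 was not available to this review. Visit timing, and possibly numbering, differs between amendments, so a comparison by visit number alone could set different days and dose steps side by side.

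**Conclusion.** The point holds in a limited form. The 5% is correct to Week 8 (+4.9%) but not as an overall figure linked to the total dose over the study (+1.4%). It also conveys nothing of the titration-phase difference: +100% to Day 3 a.m. and +32% to Day 14 a.m.

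The part that matters for interpretation is the safety output. Early results for the current titration will be mixed with those of 6 of about 25 patients (24%) on a slower schedule, and the Week 2-3 row combines different scheduled dose levels. Whether this raises, lowers or leaves unchanged the apparent early tolerability is unknown.

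The dose figures assume dosing exactly as scheduled and the SAP's own day counts. In an uncontrolled, descriptive pilot this is a modest but worthwhile improvement. It takes no position on which titration is preferable.

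**What to change.** - **SAP 4.3.** Label the 5% as the cumulative planned difference to Week 8. Add +1.4% to Week 26, and +100% and +32% to the Day 3 and Day 14 morning doses.
- **Safety output, by amendment and overall, descriptive only.** Show patients with an adverse event with onset on Days 1 to 14; patients not tolerating their starting dose, stating which dose that was; and ECG/QTc change at the titration visits, including the Week 2-3 ECG and laboratory row. Label each row with scheduled dose and day, not visit number alone.
- **Interpretation.** Base any statement on early tolerability of the amendment 2 titration on the amendment 2 column.
- **Listing 5.** Add an amendment flag.

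This needs SAP wording, one extra column in a few tables and one listing variable, all from data already collected, and follows the layout in SAP 8.2. The downside is an amendment 1 column of 6 patients, too few for any comparison beyond description.

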4.4 Blinding and unblinding

Not applicable as it is an open label study

4.5 Schedule of procedures

The schedule of procedures in amendment 2 is as follows

Table 4-1 – Schedule of procedures – Protocol amendment 2

VISIT	1	2	3		4		5	6	7	8	9
DAYS	Within 72 hours of Day 1	3	10								
WEEKS					3		8 ^{8,9}	12	16	20	26
		Virtual visit if feasible and not possible in person	Virtual visit if feasible and not possible in person		Virtual visit if feasible and not possible in person			Virtual visit		Virtual visit	
Informed Consent	X										
Demographics	X										
Medical History	X										
Clinical assessment	X						X		X		X
Vital signs ¹	X	X	X		X		X		X		X
Highest NRS pain score within the past 7 days recorded ¹¹	X		X		X		X	X	X	X	X
Review/Collection of NRS Pain Scores		X	X		X		X	X	X	X	X
12-lead ECG ²	X	X	X		X		X		X		X
C-SSRS	X						X				X
Study medication ³		XX									
Start of EP (weaning of concomitant Rx)							X				
Study Rx adjustment and accountability ⁴		X	X		X		X	X	X	X	X
Concomitant medication recording	X	X	X		X		X	X	X	X	X
AE and SAE recording ⁵	X	X	X		X		X	X	X	X	X
Laboratory	DAYS			WEEKS							
Local Laboratory	1 ⁶	3	10		3		8	12	16	20	26
CRP ¹⁰	X				X		X		X		X
CBC	X				X		X		X		X
ALT/AST	X				X		X		X		X
Alkaline Phosphatase	X				X		X		X		X
Bilirubin	X				X		X		X		X
Creatinine/ eGFR	X				X		X		X		X
INR	X				X		X		X		X
Pregnancy Test ⁷	X										

Table legend: Source: section 17.2 of protocol amendment 2

Difference between protocol amendments 1 and 2 and the (potential) impact on the statistical Analysis:

There is difference in the timing when visit 3 and week 4 visits should be performed.

Schedule of procedures was the following in Protocol amendment 1 - Table 4-2 below.

Table 4-2 – Schedule of procedures – Protocol amendment 1

Impact on statistical Analysis Plan:

Due to the difference in timing when visit 3 and the week 4 visits were planned to be performed between protocol amendment 1 and 2, this impacts on the timing when the laboratory blood draws and ECGs were performed at these visits between patients enrolled under Amendment 1 and Amendment 2 and thus may impact the following endpoints.

Efficacy endpoint

- Time to CRP normalization for patients with CRP ≥ 1.0 mg/dL at baseline

Safety endpoints

- changes in laboratory parameters, including liver function parameters and INR during the 26-week study period.
- changes in ECG parameters during the 26-week study period.

The laboratory test results, vital signs and ECG data for visit 4 (week 2) protocol amendment 1 and visit 4 (week 3), protocol amendment 2 will be combined and labelled as Week 2-3.

5 ANALYSIS POPULATIONS

5.1 Full analysis set (FAS)

All patients who were enrolled and who started the IMP will be included in the Full Analysis set.

5.2 Safety analysis set

All patients who were enrolled and who started the IMP will be included in the safety analyses set.

6 DATA REVIEW MEETINGS

Two data review meetings (DRM) will take place for this trial. The first DRM will take place to review/evaluate the data collected up to (and including) the week 8 visit and the second DRM will take place after the LPLV has taken place and prior to the locking of the clinical database.

After the DRM for the week 8, the data will be 'locked' for data collected up to this visit and will not be subsequently changed.

7 STAGED STATISTICAL ANALYSIS (SSA)

As mentioned in section 1, the analyses for this trial will be done in a staged manner – i.e. the first analysis will be performed for data collected up to the week 8 visit and the second analysis will be done when the last patient last visit is performed and the database is declared ready for complete database lock. The following data will be presented in the SSA:

- Baseline data for all patients enrolled:
 - Patient demographics: age, gender, race, ethnicity
 - Past medical history: N (%) of patients by previous episodes of pericarditis category (i.e., 2, 3, 4, or >4);
 - N (%) of patients for whom medications at baseline were prescribed for pain and pericarditis: analgesics, opiates, NSAIDs, colchicine and corticosteroids. The medications concerned will be identified as those with following

Anatomical Therapeutic Chemical (ATC) classification: H02 (Corticosteroids for systemic use), M01 (anti-inflammatory and antirheumatic products), M04 (antigout preparations), N02A (Opioids), N02B (other analgesics and antipyretics)

- N (%) of patients prescribed medications for pain and pericarditis i.e. medications which were started up to and including the Week 8 visit date and for which the stop date was either empty or > enrolment date at the time of enrolment
- CRP value at baseline will be summarized as a continuous variable
- NRS scores at baseline will be summarized as a continuous variable
- Primary efficacy endpoint, i.e. the change in patient-reported pericarditis pain using an 11-point NRS from baseline to 8 weeks – see section 8.5.1.
- Additional efficacy endpoints (see section 8.5.2):
 - Patients with normalized CRP levels (i.e. with a CRP \leq 0.5 mg/dL) at 8 weeks (for patients with CRP \geq 1.0 mg/dL at baseline) will be summarized as a categorical variable.
 - Time to CRP normalization (in days – see section 8.5.2) up to the Week 8 visit date for patients with CRP \geq 1.0 mg/dL at baseline will be summarized as a continuous variable. If CRP had not normalized at the timepoint assessed in the analysis (e.g. week 8), the patients concerned was not included in the analysis - Time to CRP normalization
 - CRP change from baseline at 8 weeks will be summarized as a continuous variable.
- Study drug exposure:
 - N (%) of patients with highest tolerated dose of (up to Week 8 visit date):
 - 10mg/kg of body weight b.i.d.
 - 7.5mg/kg of body weight b.i.d.
 - 5.0mg/kg of body weight b.i.d.

 - NRS score at baseline for patients still under medication at week 8 AND were enrolled with qualifying CRP $\geq 1.0\text{mg/kg}$ will be described as continuous variable
 - N (%) patients enrolled with CRP $\geq 1.0\text{mg/dl}$ at baseline
 - CRP value at baseline for patients enrolled with qualifying CRP $\geq 1.0\text{mg/dl}$ will be summarized as a continuous variable
 - Qualifying CRP (mg/dL) will be summarized as a continuous variable for all enrolled patients
 - For patients with a baseline CRP value $\geq 1\text{ mg/dL}$, the CRP values obtained at each visit in addition to the change from baseline at each visit will be summarized as a continuous variable. The qualifying CRP value will also be presented for the patients concerned.

8 STATISTICAL ANALYSES

The complete set of tables, figures and listings planned to be generated by this SAP is displayed in section 10.

8.1 Deviations

The total number of deviations will be reported and in addition, deviations will be presented by Important / non-important deviations.

8.2 Patient enrolment and disposition

Patient enrolment by site will be tabulated by protocol amendment and overall.

Patient disposition will be summarized by protocol amendment and overall. This will include # screened (i.e. with informed consent), # screening failures with reason, # enrolled and # who started IMP. The summary will include the number and percentage of patients in each of the defined analysis populations in Section 5. In addition, frequency counts and percentages of patients' reported reasons for ending the study will be summarized.

8.3 Description of Demographic and Baseline characteristics

A baseline variable is defined as data obtained / collected prior to or on the same day as enrollment but prior to the start of the IMP. Baseline characteristics / demographics will be summarized as either continuous or categorical variables (as appropriate) as described in section 9.1. Baseline information will be summarized for the FAS dataset only.

All demographic and baseline characteristics will be listed by study center, and patient number.

If two baseline values are available for any given variable, the closest value obtained prior to the start of the IMP will be presented as the baseline value. The baseline variables which will be tabulated are shown in the following tables:

8.3.1 Demographics

Variable label:	Comment / category labels:
Age	Take as (year of enrollment – year of birth). Tabulate as continuous variable.
Gender	Tabulate as categorical variable = male/female.
Race	Tabulate as categorical variable = American Indian or Alaska Native / Asian / Black or African American / Native Hawaiian or Other Pacific Islander / White / Unknown or not reported / other.
Ethnicity	Tabulate as categorical variable = Hispanic or Latino / Non Hispanic or Latino / Unknown or not reported

